#### **5.2.6 30 DAY POST DISCHARGE/WITHDRAWAL FOLLOW-UP**

Subjects will receive a follow-up phone call from a study coordinator and Medical Charts will be reviewed to assess if the subject was readmitted within 30 days of discharge. Follow-up phone call and Medical Chart review will instead occur 30 days after withdrawal for patients who are withdrawn prior to discharge.

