### b. Secondary Objectives

1. To measure the distribution of inspiratory flow rates with an InCheck Dial device set on measuring PIF using the medium low resistance setting in patients admitted with COPD exacerbations at Baylor University Medical Center, Dallas TX at the time of enrollment and day of discharge.
2. To determine the hospital length of stay for patients admitted with the diagnosis of COPD exacerbation.
3. To monitor and report any side effects from using once-daily ICS/LABA/LAMA or PRN therapy.
4. To evaluate the transition of care in delivering respiratory therapy medications from hospital to home.
5. To compare the number of PRN treatments, length of hospital stay, and rate of readmissions with findings in a previously analyzed historical cohort of 60 patients in our healthcare system.

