Results of an analysis of 60 patient charts randomly selected after hospitalization at Baylor University Medical Center for an exacerbation of underlying airways disease (>90% with COPD) showed tremendous variation in practice patterns; with 30% of patients receiving short-acting beta-antagonists and muscarinic agonists (SABA/SAMA) only, 70% receiving long-acting beta-antagonists (LABA) with PRN SABA/SAMA, and only 42% receiving a long-acting muscarinic agonist (LAMA), despite practice guidelines encouraging the use of SABA/SAMA only (typically 4 times daily and as needed).

It is this large variability that renders the evaluation and interpretation of institution-specific outcomes difficult. The main impetus for the proposed study is therefore to establish a more standardized open-label protocol which would allow for a more accurate assessment of intervention outcomes. As one of several secondary goals of this study, we aim to compare key outcomes (including, number of PRN treatments, length of hospital stay, and rate of readmission) with those from the historical cohort described above, when a combination LABA/LAMA/ICS inhaler is used as the primary scheduled daily inhaled therapy.

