#### 4. PATIENT POPULATION

**a. Enrollment Goal**

This study aims to enroll 80 subjects. With an anticipated acceptance rate of 2/3, this means we will approach 120 eligible candidates over that period. We estimate we will be able to achieve 30-day follow-up in 80% of enrolled patients.

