#### **d. Analysis of Secondary Endpoints**

Time (in days) in between PRN treatments, change in respiratory inspiratory flow rate from baseline to discharge, length of stay, at-home drug compliance, 30-day readmissions (all-cause and COPD/Asthma exacerbation), and 30-day survival will be compared between patients who were and were not readmitted using t-tests or chi-square tests (or Wilcoxon Rank Sum tests and Fisher's Exact tests), as appropriate.

The efficacy of the treatment protocol in the study cohort compared to the historical cohort will be assessed by comparing (1) the average number of PRN treatments per patient day while hospitalized estimated using a robust Poisson regression model (2) length of stay in the hospital, and (3) the rate of rehospitalization, using the Wilcoxon Rank sum test.

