#### **e. Reporting and Exclusions**

Missing data will not be imputed or carried forward in any of the analyses.

The sample size for continuous variables will be the number of subjects with non-missing data; in the summary of categorical variables, subjects with missing data will be excluded in the calculation of percentages.

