## **9.2 Informed Consent**

The investigator or delegated person must explain to each subject the nature of the study, its purpose, the procedures involved and any discomfort it may entail. Each subject must be informed that participation in the study is voluntary, that he/she may withdraw from the study at any time, and that withdrawal of consent will not affect his/her subsequent medical treatment or relationship with the treating physician.

The informed consent should be given by means of a standard written statement, written in nontechnical language. The subject should read and consider the statement before signing and dating it and should be given a copy of the signed document. No subject can enter the study before his/her informed consent has been obtained. The ICF must be submitted by the Investigator for IRB approval.

There will also be an option to do electronic consenting and electronic signatures by using study approved methods such as hospital telehealth system, patient iPad, telephone calls/telephone video conferencing. Documents will be sent electronically to the email address you provide for you to review the documents and sign off on.

A telephone call will be made by an authorized study research staff member to assess if the subject was readmitted within 30 days of discharge.

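### Study readmissions come from a phone call plus charts but the historical cohort is described only as a chart analysis, and no rule aligns the two sources before the rates are compared

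*Combined protocol and SAP*

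**What the plan says.** **Study cohort.** Section 5.2.6 gives two sources for 30-day readmission: "Subjects will receive a follow-up phone call from a study coordinator and Medical Charts will be reviewed to assess if the subject was readmitted". Section 9.2 repeats the call and its purpose: "A telephone call will be made by an authorized study research staff member to assess if the subject was readmitted within 30 days of discharge". For patients withdrawn before discharge, section 5.2.6 times both the call and the chart review at 30 days after withdrawal.

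**Historical cohort.** Section 3.c introduces it with "Results of an analysis of 60 patient charts randomly selected after hospitalization at Baylor University Medical Center". It mentions no contact with those patients, and it does not say how, over what window or in which records their readmissions were counted.

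**Comparison.** Secondary objective 5 (section 2.b) compares PRN treatments, length of stay and "rate of readmissions with findings in a previously analyzed historical cohort of 60 patients in our healthcare system". Section 8.7.d lists as its third comparison "the rate of rehospitalization, using the Wilcoxon Rank sum test".

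**Follow-up and missing data.** Section 4.a states: "We estimate we will be able to achieve 30-day follow-up in 80% of enrolled patients". Section 8.7.e rules out imputation and adds that "in the summary of categorical variables, subjects with missing data will be excluded in the calculation of percentages".

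Nothing in the plan limits the historical comparison to chart-found events, or adds a charts-only sensitivity analysis.

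**The concern.** A phone call added to chart review can find events but cannot remove them. A patient readmitted to an unconnected hospital can report it by phone, whereas a chart analysis may never see it. If the historical count came from charts alone, the two rates measure different things: readmission anywhere for study patients who were reached, and readmission visible in the local record for the others.

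Section 8.7.d treats this comparison as evidence on the efficacy of the treatment protocol. With equal true rates, the regimen could appear to increase readmissions; with a true reduction, part of it could be hidden. Either distortion would come from the follow-up method, not from treatment.

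**Working it through.** **Figures in the plan.** The target of 80 is accrual arithmetic: 120 approached × 2/3 accepting = 80. Expected 30-day follow-up is 0.8 × 80 = 64. The plan gives no readmission rate, no share of readmissions outside the charts, and no power calculation for objective 5. The size of the effect therefore has to be shown over assumed values.

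**Assumptions.**
- True 30-day readmission rate p = 20% in both cohorts.
- Proportion reached by phone r = 0.8, regardless of outcome. This borrows the section 4.a figure, which the plan does not define as phone reach.
- Share of readmissions not visible in the charts o = 10%, 20% or 30%.
- Historical readmissions found from charts only.
- Patients not reached are classified from their chart, so all 80 are in the denominator.

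**Formulas.**
- Historical rate = p(1 − o)
- Study rate = r·p + (1 − r)·p(1 − o)
- Artefact = study − historical = r·p·o

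| o | Historical | Study | Artefact | Ratio |
|---|---|---|---|---|
| 0% | 20% | 20% | 0 | 1.00 |
| 10% | 18% | 0.16 + 0.036 = 19.6% | 1.6 points | 1.09 |
| 20% | 16% | 0.16 + 0.032 = 19.2% | 3.2 points | 1.20 |
| 30% | 14% | 0.16 + 0.028 = 18.8% | 4.8 points | 1.34 |

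If every study patient were reached (r = 1), the artefact would be 2, 4 and 6 points.

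**Against sampling error.** With 20% in both cohorts and 80 against 60 patients, the standard error of the difference is √[0.2 × 0.8 × (1/80 + 1/60)] = 6.8 points, a 95% half-width of about 13 points. A two-sided 5% two-proportion normal approximation, which is close to a rank sum test on a yes/no outcome, gives false-rejection rates of 5.5%, 7.5% and 11.2% for o = 10%, 20% and 30%.

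**Masking.** Suppose the true rate falls from 25% (historical) to 15% (study). With complete capture in both cohorts the difference is 10 points, the ratio 0.60 and the power about 32%. With unequal capture:
- o = 10%: 14.7% against 22.5%, a difference of 7.8 points, power about 22%.
- o = 30%: 14.1% against 17.5%, a difference of 3.4 points, ratio 0.81, power about 8%.

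**With charts only in both cohorts.** Both rates are multiplied by (1 − o). Equal true rates then give a zero artefact. In the masking example at o = 30%, 10.5% against 17.5% is a difference of 7 points and the ratio is again 0.60. The absolute difference still shrinks, but the ratio is preserved.

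**The case against.** **The historical method is not described.** Section 3.c states a sampling method and a data source, not how readmissions were found. Objective 5 places the cohort within the healthcare system, so the record searched may be wider than one hospital. This stands: a bias cannot be asserted as fact, and it needs outside readmissions that the charts miss.

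**A stronger reading that the documents do not support.** A reader might infer from sections 4.a and 8.7.e that unreached patients with a clean chart would be dropped as missing while unreached patients with a readmission in the chart would be kept. On the same assumptions that would give a study rate of 23.4% to 22.7% and a ratio of 1.30 to 1.62. But section 5.2.6 joins the call and the chart review without making the review depend on a successful call. On its plain reading every subject's chart is reviewed, so an unreached patient with a clean chart has a value and section 8.7.e does not remove that patient. Section 4.a also does not say that its 80% is a phone-reach rate. Those larger ratios should not be used.

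**Direction.** It would also be too strong to say that the whole comparison is tilted against the regimen. Section 4.b excludes patients in or from critical care and those starting BiPAP after hospitalization, while section 3.c describes no such restriction for the 60 charts. Patients withdrawn before discharge are followed for less than 30 post-discharge days. Both features could lower the study rate. Only the contribution of the phone call has a known sign.

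**Size.** An artefact of 1.6 to 4.8 points is small beside a half-width of about 13 points, in an unadjusted, non-concurrent comparison that forms one part of the fifth secondary objective. This stands and limits the importance of the point. It does not excuse a systematic difference that data already planned can remove.

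**Conclusion.** The point holds in conditional form. As written, the plan compares a phone-plus-chart rate with what reads as a chart-only rate and has no rule to align them. If the historical count was chart-only and charts miss some readmissions, this feature alone raises the study rate relative to the historical one. The figures of 1.6 to 4.8 points rest on an assumed 20% true rate, 80% phone reach unrelated to outcome, and 10% to 30% of readmissions outside the charts. The effect vanishes if charts miss nothing, or if the historical readmissions were found in the same way as the study's. The comparison of readmitted with non-readmitted patients within the study is not affected by this difference between cohorts. The change is worth making before the comparison is run, but this is a secondary matter.

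**What to change.** 1. In section 8.7.d(3), base the historical comparison on chart-documented readmission within 30 days of discharge, using the same record system and the same definition in both cohorts. The denominators should be all discharged study patients and all 60 historical charts. State whether the compared rate is all-cause or cause-specific: the cause-specific label is respiratory in sections 2.d and 8.7.a, COPD exacerbation in section 8.2, and COPD/asthma exacerbation in section 8.7.d.
2. In section 5.2.6, state that a patient not reached by phone is classified from the chart.
3. For patients withdrawn before discharge, extend the chart review to 30 days after discharge for this comparison. Without this, putting them in the denominator would bias the study rate downward.
4. Record the source of each readmission (chart, phone or both), and report phone-only readmissions separately for the within-study rate.
5. State how, over what window and in which records the historical readmissions were counted.

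**Cost.** No new visits or patients are needed. The changes are wording in two sections, one added data field for the source, and a later chart check for withdrawn patients. The historical charts may need a check of window and definition, and possibly re-abstraction. The compared rates will omit outside readmissions in both cohorts, so they will understate total readmission while being found in the same way. Other differences between the cohorts remain.

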**ii. Exclusion Criteria**

- a. Clinically significant lung disease other than COPD with or without asthma.
- b. Positive SARS-CoV-2 test at the time of ED or hospital admission, or any time between admission and enrollment.
- c. History of severe hypersensitivity to milk proteins or demonstrated hypersensitivity to fluticasone furoate, umeclidinium, vilanterol, or any of the excipients.
- d. Unable to perform inspiratory flow or spirometry procedures.
- e. Critically ill patients, or patients with rapidly deteriorating or life-threatening episodes of COPD or asthma including:
  - Patients in critical care unit, or transferred from critical care unit.

- Patients who are transferred to critical care after enrollment will be withdrawn from the study and continue to receive care according to institutional standard practice.
- Patients who initiate Bilevel Positive Airway Pressure (BiPAP) after hospitalization.
  - Patients who use BiPAP at baseline (prior to COPD exacerbation) may be included if BiPAP settings remain consistent with pre-exacerbation settings. Patients will be withdrawn if BiPAP settings are changed after enrollment.

f. Pregnant or lactating women or women of child-bearing potential (WOCBP). Women must meet the non-productive potential definition below to be eligible.

➤ Non-reproductive potential is defined as:

- Pre-menopausal females with one of the following:
  - Documented tubal ligation.
  - Documented hysteroscopic tubal occlusion procedure with follow-up confirmation of bilateral tubal ligation.
  - Hysterectomy.
  - Documented Bilateral Oophorectomy.
- Postmenopausal defined as 12 months of spontaneous amenorrhea with an appropriate clinical profile (e.g., age appropriate, >45 years, in the absence of hormone replacement therapy). In questionable cases for women <60 years of age, a blood sample with simultaneous follicle stimulating hormone and estradiol falling into the central laboratory's postmenopausal reference range is confirmatory. Females under 60 years of age, who are on HRT and whose menopausal status is in doubt, are required to use a highly effective method to avoid pregnancy if they wish to continue their HRT during the study. Otherwise, they must discontinue HRT to allow confirmation of postmenopausal status prior to study enrolment. For most forms of HRT, at

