## 5. STUDY VISITS AND ACTIVITIES

### 5.1 DESIGN

This is a single-center, phase IV, post market approval prospective, open-label study evaluating outcomes of TRELEGY ELLIPTA (fluticasone furoate 100 mcg, umeclidinium 62.5 mcg, and vilanterol 25 mcg inhalation powder) on PRN nebulized short-acting beta agonist (SABA) treatment in hospitalized subjects with COPD with or without asthma.

Approximately 80 adult subjects with COPD with or without asthma will take part in this study at Baylor University Medical Center. Subjects will be given TRELEGY ELLIPTA, using the Ellipta device, placed on a consistent short-term systemic corticosteroid therapy, and followed until 30 days post hospital discharge. This study will not include patients with rapidly deteriorating or potentially life-threatening episodes of COPD or asthma.

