### **c. Analysis of Primary Endpoint**

The number of PRN respiratory treatments during hospitalization will be reported as the median [quartile 1, quartile 3] and as the average number of PRN respiratory treatments per inpatient day  $\pm$  standard deviation. A comparison between patients who were and were not readmitted within 30-days will be made using a Wilcoxon signed rank test for the number of PRN respiratory treatments. Additionally, the incident rate ratio of the average per-inpatient

day PRN treatments will be estimated using a robust Poisson regression model comparing patients who were readmitted within 30-days to those who were not.

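### For patients withdrawn in hospital, the readmission check runs from withdrawal rather than discharge, so the end of the 30-day post-discharge window can go unchecked (minor)

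*Combined protocol and SAP*

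**What the plan says.** Section 5.2.6 plans one follow-up contact, a telephone call plus a chart review, to find out about readmission in the 30 days after discharge. For one group it moves both parts: "Follow-up phone call and Medical Chart review will instead occur 30 days after withdrawal for patients who are withdrawn prior to discharge".

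Other sections describe follow-up without that exception. Section 5.1 has subjects "followed until 30 days post hospital discharge". Section 9.2 gives the purpose of the call as "to assess if the subject was readmitted within 30 days of discharge". Section 8.2 places the call used for home compliance at 30 days post-discharge.

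Withdrawal during the stay is built into the protocol. Section 4.b.ii states: "Patients who are transferred to critical care after enrollment will be withdrawn from the study". The same section withdraws patients whose BiPAP settings change after enrollment, and Section 6.4 withdraws those who test positive for SARS-CoV-2 after enrollment.

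Readmission is used in several places. Section 8.7.c says: "A comparison between patients who were and were not readmitted within 30-days will be made". Section 8.7.d uses the same grouping for the secondary endpoints, and its historical-cohort comparison includes "2) length of stay in the hospital, and (3) the rate of rehospitalization". On incomplete data, Section 8.7.e says: "Missing data will not be imputed or carried forward in any of the analyses". Section 4.a adds: "We estimate we will be able to achieve 30-day follow-up in 80% of enrolled patients".

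**The concern.** The endpoint is counted from discharge, but for this group the check is counted from withdrawal. Withdrawal comes first, so the check can fall before the window closes. Patients withdrawn for critical care transfer or a positive SARS-CoV-2 test continue under institutional care, so further inpatient days are foreseeable.

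The consequence depends on an analysis rule that the plan does not give. If these patients are analysed as followed, a readmission in the unchecked days is missed. The patient may then be placed in the wrong group in the contrasts of 8.7.c and 8.7.d, and the study's readmission count falls. If they are treated as missing or excluded, they drop out of those analyses. The rule against imputation does not say which applies to a partly observed window.

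**Working it through.** **Inputs from the documents.** Check at withdrawal + 30 days (5.2.6); window from discharge to discharge + 30 days (5.2.6, 9.2); 80 enrolled and 80% with 30-day follow-up (4.a); historical cohort of 60 (secondary objective 5).

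**Inputs not in the documents, so assumed.** Days from withdrawal to discharge (L), number withdrawn in hospital (n), 30-day readmission risk (r), and a constant readmission hazard.

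**Step 1: uncovered days.** Let W be the withdrawal day and D = W + L the discharge day. The window ends at D + 30 = W + L + 30 and the check is at W + 30. The uncovered part is (W + L + 30) − (W + 30) = L days, for L up to 30.

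| L (days) | Days covered | Uncovered share, L/30 |
|---|---|---|
| 0 | 30 | 0% |
| 5 | 25 | 17% |
| 7 | 23 | 23% |
| 10 | 20 | 33% |
| 14 | 16 | 47% |

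Coverage is complete only when withdrawal and discharge fall on the same day.

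**Step 2: is there another check?** The 30-day call in 8.2 appears to be the same follow-up call, described there for its use in measuring compliance. No other post-discharge readmission check is described.

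**Step 3: effect if analysed as followed.** Daily hazard h = −ln(1 − r)/30. Recorded risk = 1 − exp(−h(30 − L)). Missed events = n × (r − recorded risk). Percentage points = 100 × missed/80.

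| r | n | L | Recorded risk | Missed events | Points of 80 |
|---|---|---|---|---|---|
| 20% | 4 | 5 | 0.170 | 0.12 | 0.15 |
| 20% | 8 | 10 | 0.138 | 0.49 | 0.62 |
| 20% | 12 | 14 | 0.112 | 1.05 | 1.32 |
| 35% | 4 | 5 | 0.302 | 0.19 | 0.24 |
| 35% | 8 | 10 | 0.250 | 0.80 | 1.00 |
| 35% | 12 | 14 | 0.205 | 1.74 | 2.17 |

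**Step 4: effect if treated as missing or excluded.** Between 4 and 12 patients (4/80 = 5% to 12/80 = 15%) leave the endpoint. With risk rw in withdrawn patients and ro in the rest, the reported rate falls by n(rw − ro)/80. It does not change if rw = ro. With rw = 35% and ro = 20%, it falls by 4 × 0.15/80 = 0.75 points to 12 × 0.15/80 = 2.25 points. It rises if rw is below ro. This shift comes from leaving patients out, not from the timing of the call.

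**Step 5: scale.** At an assumed 20% rate, the standard error of an 80-versus-60 difference is √[0.20 × 0.80 × (1/80 + 1/60)] = 0.068, or 6.8 points. The largest value in Step 3 is 2.17/6.8 ≈ 0.32 of one standard error. Section 4.a already implies 80 × (1 − 0.80) = 16 patients without 30-day follow-up, and does not say whether these include withdrawn patients.

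**The case against.** The strongest reply is that the exception is deliberate. The heading of 5.2.6 names withdrawal alongside discharge, and its wording marks a substitution. A reader might infer that 5.2.6 flatly contradicts 5.1 and 9.2. The documents do not support that: a specific exception can sit beside a one-line design summary and a sentence on the purpose of the call. What stands is that 5.1, 8.2 and 9.2 are unqualified, and that the exception, deliberate or not, leaves part of the endpoint's window unchecked.

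A second reply is that patients withdrawn from the study may never enter the readmission analyses, in which case the timing of their call changes no reported result. That is possible. But 5.2.6 goes on collecting their follow-up, and 8.7 neither includes nor excludes them, so the absence of a rule is part of the gap.

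A third reply is that the sizes are assumed and small. That is accepted, and it sets the severity. A related caution about the remedy also stands: a patient who dies in hospital has no discharge date to count from, and a fixed-time contact after withdrawal could serve 30-day survival, whose starting point the plan does not state.

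**Conclusion.** The point holds as a minor one. Followed as written, 5.2.6 leaves the last L days of the post-discharge window unchecked for any patient discharged L days after withdrawal. That follows from the dates alone. Everything about its size rests on assumed values for the number withdrawn, L, the risk and a constant hazard. On those values, about 0.1 to 1.7 readmissions among 80 patients are missed (0.15 to 2.2 percentage points) if withdrawn patients are analysed as followed.

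Two stronger readings should be resisted. A reader might infer that the study's readmission rate is certainly too low, and so biased in its favour against the historical cohort. A lower count requires that these patients be analysed as followed and that a readmission fall in the unchecked days. The documents also do not say how readmission was ascertained in the historical cohort, so the net direction is unknown. A reader might also infer that the primary endpoint is compromised. The descriptive summaries of PRN treatments in 8.7.c do not use readmission and are unaffected; only the added contrast by readmission status is touched.

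**What to change.** In 5.2.6, time the readmission call and chart review to cover the full 30 days after index hospital discharge for every enrolled patient who has not withdrawn consent, including those withdrawn in hospital. This leaves no uncovered days for any L and brings the section into line with 5.1, 8.2 and 9.2. The contact at 30 days after withdrawal may be kept for vital status.

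In 8.7, state that withdrawn patients are counted in the readmission endpoint over that same discharge-based window, and that patients who die before index discharge are reported separately as not at risk of readmission.

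The withdrawal rules stay as they are. The cost is a later call and chart review for a few patients, and possibly a slightly higher readmission rate.
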